5.2.1.2 Summary Measures

The primary effect estimate will be the change in the ATRS from baseline to the 1-2 years visit. If the omnibus test of a treatment difference at the 1-2 years visit is significant, the estimated marginal mean change in ATRS from baseline will be displayed for the three treatment together with the p-values of the pairwise tests of the three treatment groups (See Sections 2.4.1, 2.4.2 and 5.2.1.1). If the omnibus test does not identify a treatment difference, then no pairwise testing will be performed, and no p-values will be presented. However, the 1-2 years estimated marginal mean change in ATRS from baseline will be reported for each treatment group, together with 95% confidence intervals, but these should be regarded as secondary analyses.

5.2.1.3 Assumption Checks and Alternative Analyses

Assumption checks of the fitted model will be done by visual inspection of the residuals. Marginal residuals will be plotted against the predicted marginal responses, and a check for trend will be performed. To check if the dependencies in the data has been sufficiently accounted for by the fitted

STATISTICAL ANALYSIS PLAN for the Achilles trial

model, inspection of scatter plots of conditional residuals will be done for all combinations of visits (i.e. visit 3-month vs. 6-month, 3-month vs 1-2 years and 6-month vs. 1-2 years). Normality of conditional residuals will be assessed by inspecting qq-plots for each visit.

If there are substantial deviation for normality, or there are indication of substantial residual dependence, then further random effects will be introduced in the mixed model.

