5.2 Analysis Methods

5.2.1 Primary Outcome

5.2.1.1 Primary Analysis

The primary outcome in this trial is the change in the ATRS score from baseline to the 1-2 years visit.

The primary analysis will be performed by applying a linear mixed effects model to model the longitudinal change from baseline ATRS measurements at the 3-month, 6-month and 1-2-year visits. A fixed interaction term between the follow-up visit and treatment group will be included in the model. The baseline ATRS measurement will be included as a fixed covariate in the model. Study centre, which was used as a stratification variable in the randomization, will also be included as a fixed covariate. An individual-specific random intercept term will be included in the model to account for the dependencies within individuals. An unstructured correlation structure will be assumed for the repeated measurements.

From the fitted model, the estimated marginal means will be computed for each time point and each treatment. Based on the estimated marginal means, an omnibus test, where the null hypothesis is that there is no difference between the three treatment groups, will be performed for the 1-2-year visit. This corresponds to step 1 in Section 2.4.1. If the test is statistically significant on the 5% level, pairwise testing between the three treatment groups will be performed for the 1-2-year visit (step 2 in Section 2.4.1). A 5% significance level will be used in each of these tests. As described in Sections 2.4.1-2.4.2, the hierarchical testing procedure maintains the overall type I error rate at 5%. The estimated marginal means with 95% confidence intervals of the change in ATRS from baseline will be presented for each of the treatment groups for the 1-2 years visit.

If the omnibus test at the 1-2 years visit does not show statistical significance, then no further hypothesis testing will be performed. However, the estimated marginal means and the accompanying 95% confidence intervals will still be presented, but should be considered as secondary analyses.

The analysis will be conducted in the FAS.

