5.2.4.3 Assumption Checks

Visual inspection of residual plots will be performed (qq-plots, histograms and residuals vs. fitted values). Substantial deviations from normality will be addressed by suitable transformations of the data.

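### SAP 5.2.1.3 answers non-normal or dependent residuals in the primary model by adding random effects, which repairs neither, and no other fallback is given.

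*SAP*

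**What the plan says.** Section 5.2.1.1 of the SAP uses a linear mixed model to "model the longitudinal change from baseline ATRS measurements at the 3-month, 6-month and 1-2-year visits". Two devices handle the repeated measurements: "An individual-specific random intercept term will be included in the model to account for the dependencies within individuals", and "An unstructured correlation structure will be assumed for the repeated measurements".

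Section 5.2.1.3 then sets the checks. For dependence, "inspection of scatter plots of conditional residuals will be done for all combinations of visits". For distribution, "Normality of conditional residuals will be assessed by inspecting qq-plots for each visit". One consequence follows for both failures. The trigger is worded "If there are substantial deviation for normality, or there are indication of substantial residual dependence". The only action named for it is that "then further random effects will be introduced in the mixed model".

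The section heading promises alternative analyses, but nothing else is named for the primary outcome. The five sensitivity analyses in section 5.2.1.5 deal with missing baseline values, imputation by mean or median, inverted questionnaires, treatment received and complete cases. None concerns distribution or covariance. Section 5.2.3.3 carries the primary checks over to SF-36. Only the muscle lab outcomes have a remedy aimed at non-normality (section 5.2.4.3): "Substantial deviations from normality will be addressed by suitable transformations of the data".

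**The concern.** A fallback rule should address the failure that triggers it. This one offers the same device for two different failures.

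- **Non-normality.** Section 5.1.1.2 describes a score from 0 to 100 where 100 means no symptoms, so a ceiling at the last visit is plausible. Random effects describe dependence. They do not describe skewness.
- **Dependence.** The check looks only at pairs of visits within a patient. With three visits there are three such correlations, and the model already estimates each one freely.

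The rule acts on the primary model itself. That model supplies the omnibus test, which gates every superiority claim in sections 2.4.1 and 2.4.2. The rule does not define what counts as substantial, and it does not say which or how many effects would be added. If a plot looks poor, the plan leads to a post hoc change in the primary model that may fail to converge and does not cure the problem.

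**Working it through.** **Inputs.** Three follow-up visits, a patient random intercept and an unstructured correlation (section 5.2.1.1); the checks and remedy (section 5.2.1.3); 160 completers per group, SD 20, difference 7 (section 2.3).

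**The plan's own figure.** The SAP gives no number for this rule. The sample size, used below only to judge robustness, reproduces. With group means -3.5, 0 and 3.5, the noncentrality is 160 × (3.5² + 0² + 3.5²) / 20² = 160 × 24.5 / 400 = 9.8. The power of the three-group F test at 5% is 0.804.

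**Step 1: dependence.** Three visits have 3 variances and 3 covariances, 6 terms in all. Let R be the residual matrix, s the intercept variance and J a matrix of ones. The modelled covariance is V = R + sJ.

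| Model | Visit-specific variances | One common variance |
|---|---|---|
| Unstructured only | 6 parameters | 3 + 1 = 4 |
| + random intercept | 7 | 5 |
| + random intercept and slope | 9 | 7 |

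In the first column, unstructured alone already fits all 6 terms, so nothing added is identifiable. In the second, the intercept is still redundant, because 4 parameters already give every common-variance matrix. A slope can then change the visit variances, but the correlations were free from the start.

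**Step 2: illustration.** These are simulated data, with settings that are assumptions: 480 patients, scores clipped at 0 and 100, a ceiling at the last visit.

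| Model | Log-likelihood | Correlations (3 m–6 m / 3 m–last / 6 m–last) | Skewness, last visit (normalised residuals) |
|---|---|---|---|
| Unstructured, visit-specific variances | -5974.465 | 0.432 / 0.491 / 0.593 | -0.51 |
| + intercept | -5974.465 | unchanged | -0.51 |
| + intercept and slope | -5974.465 | unchanged | -0.51 |
| Unstructured correlation, common variance | -5984.323 | 0.430 / 0.494 / 0.604 | -0.35 |
| + intercept | -5984.323 | unchanged | -0.35 |
| + intercept and slope | -5974.837 | 0.432 / 0.495 / 0.589 | -0.50 |

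In the last row the SDs move from 17.55 at every visit to 18.7, 17.7 and 15.8. That accounts for the better fit. Skewness does not improve.

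**Step 3: normality.** A sum of Gaussian random effects and Gaussian errors is Gaussian. However many effects are added, the implied outcome is multivariate normal. This does not depend on the simulation.

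**Step 4: the check itself.** With y the deviation from the fitted mean, the predicted intercept is s·1′V⁻¹y. The conditional residual is therefore y − sJV⁻¹y = RV⁻¹y, with covariance RV⁻¹R. This is not diagonal in general. It also depends on how V is split into R and sJ, and the data cannot determine that split. For a correctly specified Gaussian model with assumed R (variances 300, 250, 200; covariances 90, 60, 120), simulated conditional residuals had these correlations between visits:

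| Intercept variance | 3 m–6 m | 3 m–last | 6 m–last |
|---|---|---|---|
| 30 | 0.26 | 0.16 | 0.48 |
| 60 | 0.21 | 0.09 | 0.43 |
| 100 | 0.15 | 0.01 | 0.37 |

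The scatter plots can therefore suggest dependence when nothing is wrong.

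**Step 5: SF-36.** There are two follow-up visits, so 2 variances and 1 covariance. If the same model is used with visit-specific variances, 4 parameters face 3 terms.

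**The case against.** Four points on the other side deserve weight.

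1. **The counts depend on a reading.** Section 5.2.1.1 speaks of correlation, not covariance. A reader might infer from the counts of 7 and 9 that no further random effect could ever do anything. The SAP does not support that. With one common variance, a slope would correct unequal visit variances, and in the illustration the last-visit SD changes by a factor of 17.55 / 15.8 = 1.11. This stands, but unequal variance is not one of the two stated triggers. A random effect at another level, such as surgeon, could model dependence between patients, but the planned plots do not look for it.
2. **The harm is small.** A reader might infer that the primary test is invalid or its type I error inflated. Nothing shows this. If a redundant effect converges, the marginal fit and the treatment contrasts are unchanged, and contrasts of means with about 160 per arm are fairly robust to moderate skewness. Non-convergence is a possibility that was not demonstrated.
3. **The skewness figures are for normalised residuals**, whereas the SAP inspects conditional ones. This is correct. The argument in step 3 does not need those figures. Adding effects can change what the conditional plots show without changing a saturated fit.
4. **A conditional switch to robust inference would be just as post hoc.** This is right, and the fix avoids it.

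A reader might also suspect the muscle lab section. It uses linear regression without random effects and names a transformation, so it does not share this defect.

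**Conclusion.** The point holds. The rule in section 5.2.1.3 cannot repair either condition that triggers it, and the SAP names no other fallback for the distribution or covariance of the primary outcome. Part of the problem lies in section 5.2.1.1, where the random intercept duplicates what the unstructured structure already does and leaves the conditional residuals poorly defined.

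The practical size is moderate to small: a possible convergence failure and an unspecified, plot-driven change to the model behind the gating test. The conclusions on correlation and normality rest on three visits and Gaussian effects, which is how a linear mixed model is ordinarily read. The claim that extra effects are not identifiable also requires visit-specific variances. The simulated values are illustrations only. The plan should be corrected because the rule is wrong as written, not because a biased result has been shown.

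**What to change.** - **Section 5.2.1.1:** specify an unstructured covariance over the three visits with visit-specific variances, and remove the random intercept. State that this model is primary whatever the plots show.
- **Section 5.2.1.3:** delete the rule on further random effects. Base the distribution and dependence checks on normalised residuals (marginal residuals scaled by the fitted covariance), reported as description only.
- **Section 5.2.1.5:** add one sensitivity analysis that is always reported: the omnibus and pairwise tests at 1-2 years with patient-level cluster-robust (sandwich) standard errors. Keep the pairwise tests under the same gate as in the primary analysis.
- **Section 5.2.3:** make the same changes for SF-36, which takes over these checks.

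The cost is a change of SAP wording and one additional analysis. No new data are needed, and section 5.2.4.3 can stay as it is.

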5.2.1.4 Missing Data

At baseline and at the three follow-up visits (3-month, 6-month and 1-2-year), patients answer the ATRS questionnaire. Each questionnaire contains ten questions, and each question is answered on an 11-point Likert scale ranging from 0 to 10. The total score is calculated by summing the individual Likert items. For each question, the value is set according to the guidelines in the ATRS manual (8). Importantly, if at least one of the 10 questions lack an answer, the ATRS is regarded as missing for the patient for that particular visit.

Missing baseline ATRS data will be imputed using mean imputation (9). If baseline ATRS are skewed, median imputation will be used instead.

Missing values in follow-up ATRS measurements (at the 3-month, 6-month and 1-2-year visits) will be handled by the mixed modelling approach. However, individuals with no follow-up measurements will then be excluded from the analysis. If the proportion of patients that has no follow-up measurements is less than 5%, no action will be taken to include these in the analysis. If this proportion is larger than 5%, multiple imputation will be used to impute the 1-2 years ATRS for these individuals.

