5.2.1.5 Sensitivity Analyses

The following sensitivity analyses will be performed:

1. If there are patients with missing baseline ATRS, a sensitivity analysis will be conducted in the patients that has baseline a measurement (i.e. excluding the patients with missing baseline measurement).
2. If the missing baseline ATRS measurements were imputed using median imputation (see Section 5.2.1.4), a sensitivity analysis will be conducted using mean imputation instead.
3. The ATRS questionnaire is known to sometimes be misinterpreted, and inverted, by patients (10, 11). If the study group suspects that this has happened for one or more patients at any time point, a sensitivity analysis will be conducted where these possibly inverted ATRS measurements are inverted back. I.e. if a patient e.g. has answered the value 2 on an item in the questionnaire, this is converted to $10-2=8$. This is only done for patients where the study group suspects that the scale has been inverted.
4. A sensitivity analysis will be conducted in the PPS, the per protocol set. That is, if any patients received a different treatment than randomized to, they will in this sensitivity analysis be placed in the treatment group corresponding to the treatment they actually received.
5. A sensitivity analysis will be conducted in patients that has complete follow-up ATRS measurements, the complete case set (CCS).

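### If baseline ATRS values are missing and skewed, the switch to median imputation slightly shifts each arm's reported mean change; the comparisons between arms are essentially untouched

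*SAP*

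**What the plan says.** Section 5.2.1.4 makes mean imputation the default for a missing baseline ATRS and then switches: "If baseline ATRS are skewed, median imputation will be used instead". It gives no criterion for skewness and does not say whether the mean is taken over all arms. A score counts as missing if any one of the ten items is unanswered.

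The imputed value is used twice in the primary model. Section 5.2.1.1 defines the outcome as a change: "The primary outcome in this trial is the change in the ATRS score from baseline to the 1-2 years visit". It also adjusts for baseline: "The baseline ATRS measurement will be included as a fixed covariate in the model".

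The reported quantity is a mean for each arm: "The estimated marginal means with 95% confidence intervals of the change in ATRS from baseline will be presented for each of the treatment groups". Section 5.2.1.2 states: "The primary effect estimate will be the change in the ATRS from baseline to the 1-2 years visit". If the omnibus test is not significant, the per-arm values are still reported, but as secondary analyses.

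Section 5.2.1.5 plans two relevant checks. Item 1 drops patients without a measured baseline. Item 2 reads: "If the missing baseline ATRS measurements were imputed using median imputation (see Section 5.2.1.4), a sensitivity analysis will be conducted using mean imputation instead".

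For SF-36, also analysed as change from baseline, section 5.2.3.4 uses mean imputation with no median switch.

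**The concern.** Filling in a missing baseline covariate with a single constant is acceptable in a randomised trial because the same constant goes to every arm. That argument does not need a symmetric distribution, so skewness is not in itself a reason to leave the mean.

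Here the constant also enters the outcome. The reported quantity is a mean change, and subtracting a median from some patients' follow-up scores displaces it. The displacement is zero when mean and median coincide and grows with the gap between them, so the rule moves away from the mean only where doing so matters. The version that preserves the mean then becomes the sensitivity analysis.

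At stake are the per-arm mean changes and the position of their confidence intervals, not the choice between treatments.

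**Working it through.** **Inputs from the SAP.** Change from baseline as outcome, baseline as covariate, per-arm marginal means (5.2.1.1, 5.2.1.2); mean imputation with a median switch (5.2.1.4); SD 20, target difference 7, 160 completers per arm (2.3). The SAP has no figure for the imputation point itself. Its sample size reproduces: a three-group one-way ANOVA with extreme means 7 apart and the third midway needs 159 per group, and power at 160 is 0.804.

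**Inputs not in the SAP (assumed).** Share of baselines missing, p; mean–median gap of baseline ATRS.

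**Step 1: average imputed baseline.** Let m be the observed mean, d the observed median and c the imputed constant. The average is (1 − p)·m + p·c.
- With c = m it equals m.
- With c = d it equals m + p·(d − m).

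**Step 2: reported mean change.** Because baseline is a covariate, the marginal mean change is the adjusted follow-up mean minus the average imputed baseline. With similar missingness across arms the adjusted follow-up mean does not move, so the shift in each arm is p·(m − d). A left-skewed baseline (m < d) makes the reported change too low; a right-skewed one makes it too high.

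**Step 3: size of p × gap, in ATRS points.**

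| Missing | gap 2 | gap 5 | gap 10 |
|---|---|---|---|
| 2% | 0.04 | 0.10 | 0.20 |
| 5% | 0.10 | 0.25 | 0.50 |
| 10% | 0.20 | 0.50 | 1.00 |

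A deliberately extreme 20% missing with a 15-point gap gives 3.0.

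**Step 4: simulation.** 3,000 runs per setting, 160 per arm, no treatment effect, follow-up-on-baseline slope 0.3. Change at 1–2 years was regressed on arm, imputed baseline and centre, with complete follow-up. This simplifies the planned mixed model.
- Left-skewed baseline (mean 88.0, median 91.7), 10% missing in each arm: median imputation shifted the arms by −0.37. The formula gives 0.10 × (88.0 − 91.7) = −0.37.
- Right-skewed baseline (mean 15.0, median 10.4), 10% missing: about +0.46. The formula gives 0.10 × 4.6 = 0.46.
- Mean imputation: bias of at most 0.012 points in any setting.

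A smaller check used a three-visit mixed model with random intercept and about 8% missing visits (60 runs, gap −5.2, 10% of baselines missing). Median imputation shifted the arms by −0.49 to −0.54, against a predicted −0.52. Mean imputation stayed within 0.04.

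**Step 5: differences between arms.** If arms g and h have missing shares p_g and p_h, and b is the follow-up-on-baseline slope, the difference moves by about b·(p_g − p_h)·(m − d).
- Equal shares: zero (simulated, within 0.01).
- 15/5/10% missing, right skew: 0.3 × 0.10 × 4.6 = 0.14 (simulated 0.135, the largest in this pattern).
- 30/0/0% missing: 0.3 × 0.30 × 3.7 = 0.33 and 0.3 × 0.30 × 4.6 = 0.41 in absolute value (simulated 0.32 and 0.41).

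Omnibus type I error was 0.038–0.057 under median imputation and 0.039–0.056 under mean imputation in the same runs.

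**Step 6: scale.** With SD 20 and 160 per arm, the standard error of an arm mean is 20/√160 = 1.58 and the 95% half-width is 1.96 × 1.58 = 3.1. A shift of 1.0 is about a third of that half-width and 1.0/7 = 14% of the target difference. A shift of 0.04 is negligible on either scale.

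**The case against.** The strongest objection is that no decision rests on the affected quantity. The objective in 1.2.1, the hypotheses in 2.4.1 and the superiority claims in 2.4.2 all concern differences between arms, and a constant common to all arms cancels. This stands, and it is why the point is minor. A reader might infer from the displaced means that the omnibus test or the treatment comparison is biased. The documents do not support that: allocation is 1:1:1 and randomised, nothing suggests that baselines are missing at very different rates by arm, and the calculation shows essentially no effect when rates are similar.

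A second objection is that the SAP already plans the remedy, because under item 2 of section 5.2.1.5 "a sensitivity analysis will be conducted using mean imputation instead". That rerun would make the shift visible. It would still leave the shifted version as the primary result and the other as the check, so it limits the harm without correcting the rule.

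Third, the median has something in its favour. Item 3 of section 5.2.1.5 acknowledges that patients sometimes invert the ATRS scale, and inverted scores are corrected only in a sensitivity analysis. Such values pull the mean and hardly move the median. This is a fair reason to look at a robust value, but it is not the reason that the SAP gives for the switch, and a sensitivity analysis can serve it.

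Finally, mean imputation is not unbiased under every mechanism. If patients without a baseline differ systematically in their true baseline, neither constant is right for the per-arm means. The median does not repair that.

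**Conclusion.** The point holds in limited form. If some baselines are missing and the observed baseline is skewed, the median switch displaces each arm's reported mean change by about (share missing) × (mean − median). Both conditions are needed. Equal displacement across arms also needs similar missingness, and the statement that the mean avoids the problem needs baselines missing independently of their value.

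Under assumed values of 2–10% missing and gaps of 2–10 points, the displacement is about 0.04–1.0 points. Neither input is in the SAP, so this is a range of assumptions and not an estimate for this trial. Tests and differences between arms are essentially unaffected when missingness is similar; in the settings simulated they moved by a few tenths of a point at most, and that only under very unequal missingness. It would be wrong to conclude that every arm will be biased, or that the trial's conclusions are at risk. This is a minor improvement, worth making because it is so easy.

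**What to change.** In section 5.2.1.4, use the overall observed mean of baseline ATRS, pooled over arms, as the primary imputation whatever the shape of the distribution. This brings ATRS into line with section 5.2.3.4 for SF-36 and removes a data-dependent choice that has no stated criterion.

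In section 5.2.1.5, either delete item 2 or reverse it, so that median imputation is the sensitivity analysis. Keep item 1.

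The cost is a sentence or two of editing and no extra analysis. The one small downside is that the mean is more sensitive than the median to inverted or outlying baseline scores. A median sensitivity analysis, together with the existing item 3 on inverted scores, would show whether that matters.
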